STU#: 00212165

PROTOCOL TITLE: Targeted Melanoma Detection with Skin Self-Examination During COVID-19 Restricted Physician Access

PRINCIPAL INVESTIGATOR:

[name]
Northwestern University Feinberg School of Medicine
Department of Dermatology
[name]
[name]
[contact]
[contact]

RESEARCH PERSONNEL:

[name], MS
[name], BS

STATISTICIAN:

[name]
Professor of Preventive Medicine
Northwestern University Feinberg School of Medicine

VERSION DATE:

April 2, 2020

NCT04420273

STUDY SUMMARY:

The purpose and overarching aim of this study is to reduce melanoma mortality by improving early detection of melanoma with skin self-examination among people who self-identify as being at risk. Self-management of melanoma detection with skin self-examination (SSE) depends on ready access to dermatologists when a concerning mole is detected. In March 2020, the Illinois stay at home order (COVID-19) removed ready physician access and prohibited non-essential health care. Additionally, there was uncertainty about when regularly scheduled health care would resume. This submission seeks to explore the feasibility of at-home non-invasive mole self-sampling for those with a concerning mole with the intention of providing recommendations about the need for the mole to be biopsied.

OBJECTIVES:

Aim 1: To assess the effectiveness of targeted melanoma detection (TMD) with SSE education delivered remotely to women who had a screening mammogram.

The effect of TMD with SSE education on a) SSE performance, b) identification of concerning moles, c) time between noticing a concerning mole, requesting a mole self-sampling kit and receiving health care, and d) SSE sustainability in comparison with controls will be assessed among women served by Northwestern Medicine in one rural community and one metropolitan community. Health care providers' (HCPs) clinical/pathologic assessment of concerning moles will be identified in the Northwestern Medicine electronic health record (EHR) system.

Exploratory Aim: To assess the feasibility of self-sampling concerning moles for gene assay.

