Contact information for potential subjects, who will be women who had a screening mammogram from January 2, 2019 until February 28, 2020, will be obtained from the Northwestern Medicine Electronic Data Warehouse (EDW). Based on our experience, women with a history of breast cancer will be excluded because the focus of their health care is on treatment of breast cancer. Subjects will be emailed a recruitment email explaining the research study regarding skin cancer prevention and skin self-examinations. Subjects will receive a link to the online REDCap program that offers electronic consent, randomization, and self-reported surveys. After remotely enrolling in the study, and completing the baseline questionnaire, the subjects will be randomized 1:1 between intervention and control arms. Intervention arm participants will receive the SSE brochure. The SSE brochure discusses basic information about melanoma, how to identify a melanoma, the importance of a skin check partner, and gives a diary for tracking monthly changes in moles via a provided scorecard. The provided postcard maybe printed by the woman and affixed to a location in their homes to capture their attention and remind participants to perform SSE. Subjects will invite a skin check partner to help score the border, color, and diameter of a new and/or concerning mole(s) using a provided scoring system for their 4 months of study participation. While a skin check partner will be beneficial to perform SSE, a skin check partner is not an absolute requirement to participate in this research. The scoring system uses a scale of 1-3 (1= normal, 2= unsure, 3= not normal). In the brochure, color examples of normal and abnormal features illustrate the scoring rules. The decision rules about seeking health care are based on the cumulative score of three features of the mole: 3 = benign, stop checking the mole; 4-7 = check the mole in one month; 8-9 = make an appointment with a doctor to have the mole checked in about 2-3 weeks, which is the standard of care for evolving moles. In the absence of physician access (COVID-19), the decision rules used in our prior research will be modified to:
8-9= perform mole self-sampling to determine if the mole needs to be biopsied.

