In our prior research, women have checked moles of family members, especially the male spouse. We will extend the opportunity for the women enrolled in the study to sample the concerning moles of their skin check partner. If throughout the 4 months of the intervention arm's active engagement in skin self-examinations, participants indicate that they found a concerning mole on their skin check partner while performing a partner skin exam, an opportunity for the mole of the partner to be self-sampled (or sampled by the participant) will be offered. For mole self-sampling to occur, the subject would first be asked eligibility questions to ensure they are over the age of 18. Once the age is established, the partner will be required to sign an electronic consent form, indicating what information will be collected and what information will be shared with them and their HCP.

Participants who have selected the self-sampling kit will be invited to participate in a structured telephone exit interview. The exit interview will seek to obtain feedback from the participant on the process of self-sampling and gain feedback on study materials.

PROCEDURES INVOLVED:

Enrollment to intervention or control arms, randomization, will be automated in REDCap using a specific formula generated by the performed Northwestern University's Department of Preventative Medicine statistical team. The randomization of subjects who had screening mammograms at Northwestern Medicine Kishwaukee Community Hospital Breast Center and Northwestern Medicine Lynn Sage Comprehensive Breast Center will continue until about 500 women are enrolled from each location. De-identified data will be reviewed by the study's statistical team to ensure there is an equal distribution of subjects at each site in both the intervention and control arm.

In the intervention arm (Group 2), the participant will receive the SSE brochure and SSE postcard after consenting online and completing baseline assessments. Upon request,

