Design, Analysis, and Power Calculation with Target Enrollment Justification

For the RCT, participants will be randomly assigned to receive the SSE intervention or control (healthy lifestyle) in a 1:1 ratio. This will result in approximately 500 participants in each group. The primary analysis will be intent to treat, with data imputed one of two ways. First, we will run a “worse-case scenario” where all drop-outs will be assumed to not be performing SSE. Second, we will create 5 imputed data sets for missing data based on all available data and analyze with PROC MIANALYZE to obtain valid statistical inferences. From previous work, we expect at least 60% retention at 4 months.

We will use GLMM with a logit link to test if the intervention affects the rate of SSE, while adjusting for the repeated measures within individuals over the first 4 months. Using these repeated measures, and assuming an autocorrelation of 0.9, a total sample of 1000 would enable us to detect an increase from 80% of SSE in the control group to 86.3% in the intervention group. Assuming only 10% discordance, a sample of 500 control women provides 80% power to detect an increase of 7%, while the remaining 3% cease SSE. Additional fidelity measures in Aim 2 will be combined to score an overall standardized fidelity score at each time. If the mean fidelity score is 80%, a sample of 500 women provide enough information to produce a 95% Confidence interval with a width of 0.09. The sample for 500 intervention women provides 80% power to detect declining fidelity or sustainability of monthly SSEs as a standardized slope of 0.13. The secondary outcome of seeking HCP appointments for a necessary mole will be analyzed with generalized linear models, as described above, but considering the outcome as “any HCP appointment” during the study time frame. Previous data suggests that approximately 14% of women should contact HCP for an appointment, and our sample of 1000 women provides 80% power to detect a baseline rate in the control group as small as 21%.

Plans for securing the data is in the “provisions to protect the privacy interests of participants” section of the protocol.

PROVISIONS TO MONITOR THE DATA TO ENSURE THE SAFETY OF PARTICIPANTS:

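### Equal arms within each site are left to a data review; no site-stratified allocation is stated and no site term is named in the models

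*Combined protocol and SAP*

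**What the plan says.** - **Ratio.** Study Interventions says that after the baseline questionnaire "the subjects will be randomized 1:1 between intervention and control arms". The section on design, analysis and power says that "participants will be randomly assigned to receive the SSE intervention or control (healthy lifestyle) in a 1:1 ratio" and adds: "This will result in approximately 500 participants in each group".
- **Method.** Under Procedures Involved, allocation "will be automated in REDCap using a specific formula generated by" the statistical team. The formula is not described. It could be simple, blocked, stratified or minimised.
- **Site totals.** The same paragraph says that randomisation "will continue until about 500 women are enrolled from each location".
- **Balance by site.** The next sentence assigns this to a review: "De-identified data will be reviewed by the study's statistical team to ensure there is an equal distribution of subjects at each site", in both arms. It gives no timing, no degree of imbalance that would prompt action, and no permitted action.
- **Sites.** Under Objectives, the comparison is made "among women served by Northwestern Medicine in one rural community and one metropolitan community".
- **Model.** The primary GLMM is described as adjusting for repeated measures within a woman. Site is not named there, nor in the generalized linear model for appointments with a health care provider (HCP).

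**The concern.** The plan sets a target for the design (equal arms within each site) but names a monitoring step as the way to reach it. Balance comes from the way the list is built, and looking at the data can only show whether it was achieved. If the list is not restricted by site and someone is nonetheless expected to secure equality, the only levers left are later assignments or who is enrolled. Using either would make part of the allocation depend on a decision taken after seeing earlier assignments.

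Site is worth balancing because one community is rural and the other metropolitan, and access to care bears on the secondary outcome of HCP appointments. The documents give no figure for how skin self-examination (SSE) or appointments differ by site, so any such difference below is an assumption. As written, neither the stated allocation nor the stated models deal with site.

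**Working it through.** **1. The plan's own figure.** The plan says that 1000 women can detect 80% against 86.3%, with autocorrelation 0.9 over four monthly measures. Two-sided alpha of 0.05 and 80% power are assumed for this figure, because the sentence gives neither.

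- Exchangeable correlation: variance factor (1 + 3 × 0.9)/4 = 0.925. Effective n per arm is 500/0.925 = 540.5, power 79.1%, detectable rate 86.4%.
- AR(1) correlation: factor [4 + 2(3 × 0.9 + 2 × 0.81 + 0.729)]/16 = 0.881. Effective n is 567.5, power 81.0%, detectable rate 86.2%.

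The stated 86.3% lies between the two, so it is reproduced. It rests on 500 per arm and is not in dispute.

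**2. Imbalance if allocation were simple.** This is a conditional check, since the documents do not say that allocation is simple. With 500 women at a site, the number in one arm is X ~ Binomial(500, 0.5).

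- SD = √(500 × 0.25) = 11.2, and the 95% range is 228 to 272.
- For a split of k:(500 − k) or worse, p = 2 × P(X ≥ k). For one or both sites, the probability is 1 − (1 − p)².

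| Split or worse | One site | One or both sites |
|---|---|---|
| 260:240 | 39.6% | 63.5% |
| 265:235 | 19.5% | 35.1% |
| 270:230 | 8.1% | 15.5% |

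Exactly 250:250 has probability 3.6% at one site and 0.036² = 0.13% at both. Simple allocation therefore does not give equal arms by site.

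**3. What imbalance costs in power.** Power = Φ{[0.063 − 1.96√(p̄q̄(1/n₁ + 1/n₂))] / √(p₁q₁/n₁ + p₂q₂/n₂)}, where p̄ is the pooled rate and q = 1 − p. The gain from repeated measures is left out.

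- 500:500 gives (0.063 − 0.0464)/0.0236 = 0.704, so power is 75.9%.
- 544:456 (both sites at 272:228, the control arm larger) gives 75.3%.

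The loss is 0.6 percentage points.

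**4. What imbalance could do to an unadjusted difference.** Suppose the sites lean in opposite directions at their 95% limits (272:228 and 228:272). The arms are then 500:500, but the share of women from one site differs between arms by 44/500 = 0.088. An assumed site difference in SSE of 5, 10 or 20 points shifts the crude arm difference by 0.4, 0.9 or 1.8 points. The plan's detectable difference is 6.3 points. This is an unlikely corner case, and a site term in the model would deal with it.

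**5. With site-stratified permuted blocks.** Within a site, the arms can never differ by more than half the largest block. For assumed block sizes of 4 to 8, that is 2 to 4 women at any time, with no correction needed.

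**The case against.** The strongest reply is that the protocol does name an allocation mechanism, an automated REDCap formula written by the statistical team. A 1:1 ratio describes stratified blocks as well as it describes coin-tossing. The team that writes the formula also reviews the data, so the natural reading may be a check that the formula is working. Women enrol themselves online and are randomised after the baseline survey, and no recruiter who chooses assignments is described. Dependence of later assignments on earlier ones is not in itself a fault, since permuted blocks have it too. Chance imbalance under valid randomisation is not bias, and the loss of power is trivial.

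Most of this stands. A reader might infer that randomisation is simple, that the team will watch accruing data, and that it will correct assignments by hand. The documents support none of these. They do not describe the formula, give no timing for the review, and mention no trigger or correction.

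Two things survive. If the formula is stratified, the protocol omits the feature that would meet its own target and gives the credit to a review. If it is not, the target has no mechanism behind it. On either reading, the review's limits are unstated and no site term is named.

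**Conclusion.** The point holds as an inexpensive improvement. It does not show that the plan is wrong as written. The allocation method is unspecified, and the one step said to deliver equal arms by site cannot do so by itself.

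The imbalance figures (about 8% at one site and 16% at one or both for 270:230 or worse) assume simple 1:1 allocation, independent between sites, with exactly 500 women at each. They do not apply if the formula is already restricted by site. Even under simple allocation, the power loss is under 1 percentage point. The shift of 0.4 to 1.8 points in the crude difference needs both sites at opposite extremes and an assumed site effect.

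The case therefore rests on delivering the balance the plan asks for and on ruling out changes to the allocation. It does not rest on precision or on any demonstrated bias. It would go too far to say that the target can be met only by altering assignments, because that is true only if the undescribed formula does not balance by site.

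**What to change.** 1. Under Procedures Involved, describe the formula. Suggested text: *The allocation list is computer-generated in randomly permuted blocks of varying size, stratified by site, and is loaded into REDCap before the first enrolment.*
2. Redefine the review. Suggested text: *The statistical team's review of numbers by site and arm is a check only; no assignment is changed as a result.*
3. In the design and analysis section, add site as a fixed term in the primary GLMM and in the HCP-appointment model.

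If the formula is already stratified by site, say so in place of item 1 and make only items 2 and 3.

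The cost is negligible before launch. Randomisation is already automated, and the location of each woman's mammogram is among the data drawn from the data warehouse, so site is known before allocation. The work is to build the list by site and edit a few sentences. The sample size does not change.

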Subjects in the intervention arm will monitor new and concerning moles for 4 months by doing monthly skin checks and partner-assisted skin checks (if applicable), record the scores on a scorecard provided in their SSE brochure, and complete the monthly online survey, which asks about changes in mole scores and potential anxiety associated with evolving moles. Subjects will also receive a monthly text message to their personal phone with SSE reminders.

If the subject indicates on their monthly survey or by communicating with the study team, in the form of an email and/or call, that the score of their mole has increased, three options on how to proceed will be offered to the subject. The three choices are as follows: a) continue monthly checking the mole for change, b) receive the mole self-sampling kit to obtain genetic analysis to guide the decision to seek health care, or c) seek an appointment with an HCP.

The mole self-sampling kit contains the materials, directions and a Fed Express or USPS Express mail envelop to overnight the kit to the DermTech laboratory.

Participants may request a kit by email or telephone call to the research team, who will send the kit by Fed Express or USPS Express mail. Within 3-5 business days, the DermTech laboratory will provide the results of the gene analysis online to the PI, [name], who will inform the participant with a written report stating:

- a) the mole is benign, and nothing further is needed or
- b) the mole needs to be biopsied.

If the initial sample has too few cells for analysis, then the participant will be invited to obtain another sample, instructions will be reviewed by telephone or by Facetime with the participant and an additional sample will be obtained.

Participants requiring a skin biopsy will be referred to a local HCP. The research team will develop a participant navigation system for triage to a local HCP, including surgical oncologists, dermatologists, and family practitioners. This triage system will be used to refer participants to schedule an appointment for the skin biopsy within 2-3 weeks. The genetic analysis of the mole will be provided in a letter to the HCP selected by the participant.

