a printed brochure will be mailed. Participants will receive monthly reminders via email and text messaged to their personal phone to perform SSE, to encourage engagement and retention. In addition, a monthly REDCap survey will be sent to the subject's email. This monthly survey will include goal setting and reminders to engage a skin check partner to help check skin in hard to see areas and to assist with the monitoring of any concerning moles and new moles. Tracking of specific details and changes of concerning and new moles will be documented on the provided scorecard in the brochure. If the score of the mole increases, which is indicated on the monthly survey or via email and/or phone, three options on how to proceed with the concerning mole will be provided to the subject.

-Option 1 is to continue monitoring the mole monthly for change.

-Option 2 will be to perform mole self-sampling with the kit to collect a sample of surface cells of the concerning mole with four adhesive patches for gene analysis to help decide about seeking further health care for biopsy of the mole. Of note, physician collected samples tested for *LINC* and *PRAME* gene mutations differentiated melanoma and melanoma in situ from benign moles and were confirmed histologically with 91% accuracy.

-Option 3 will be to seek an appointment with a health care provider.

If mole self-sampling is selected, the kit with the subject number as ID (blinded for personal identifying information), directions, and postage for the kit to be sent to the company that created this self-sampling kit, DermTech, will be provided. Upon completing the mole self-sampling and mailing the specimen to the DermTech laboratory, it will take 3-5 days for the results to be provided to the PI, [name], in the form of a secure online portal. The subject will not obtain their gene test results from the DermTech laboratory. [name] will provide written test results to the participant with the option of discussing the results with a telephone call. A referral will be made to the HCP to perform a skin biopsy if needed. The DermTech self-sampling kit is approved for use but requires ordering by a licensed HCP, who will be [name], the PI.

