If the option to see the HCP is selected, the research team will assist with locating one and will remind the subject that the HCP may not be available for some time. The study team will not cover the cost of seeing the HCP or cost of treatment recommended by the HCP. The non-payments details are explicitly stated in the consent document.

If the mole(s) requires a biopsy and/or treatment, the EHR will be reviewed to identify diagnosis codes of the mole and review HCP notes.

If throughout the 4 months of active engagement in skin self-examinations, a participant in the intervention arm indicates that they found a concerning mole on their skin check partner while performing a partner skin exam, an opportunity for the concerning mole of the partner to be self-sampled will be offered. For the self-sampling to occur, the subject (the skin check partner) would first be asked eligibility questions to ensure they are over the age of 18 and meet basic eligibility criteria. Once eligibility is established, the partner will be sent an electronic consent form, via REDCap, and complete and sign the form,

indicating they understand what is expected of them as a research participant and the information that was presented to them in the consent document. The same process will be followed for the skin check partner as is in place for the research subject.

Controls (Group 1) will receive a healthy lifestyle brochure and a healthy lifestyle postcard after consenting online and completing baseline assessments. After enrolling in the study, a baseline survey will populate in REDCap, and the subject will be able to download a healthy lifestyle brochure and the postcard reminder. Upon request, the brochure will be mailed. Each month, the subject will receive an email to complete the monthly survey and will receive healthy lifestyle text messages to their mobile phone. The survey they receive will mirror the survey of the SSE intervention arm; therefore, awareness of SSE will be expected to increase, and SSE may be initiated among controls. If a subject indicates that they have found a concerning mole on their monthly survey, the subject will be advised to reach out to their health care provider for further assessment. After completing the final monthly survey, controls will be offered the SSE brochure.

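### Only the intervention arm is given a retention-motivated reminder email, and one of two undifferentiated primary imputation rules would turn any retention difference between arms into an apparent SSE difference

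*Combined protocol and SAP*

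**What the plan says.** **Intervention contacts.** The section on procedures involved (Group 2) states: "Participants will receive monthly reminders via email and text messaged to their personal phone to perform SSE, to encourage engagement and retention". The survey is a further contact: "In addition, a monthly REDCap survey will be sent". The section on study interventions describes the reminder differently, as a text alone: "Subjects will also receive a monthly text message to their personal phone with SSE reminders". The two sections do not agree on whether there is a reminder email.

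**Control contacts.** For Group 1, the section on procedures states: "Each month, the subject will receive an email to complete the monthly survey and will receive healthy lifestyle text messages to their mobile phone". It mentions no separate reminder email and no retention purpose.

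**Analysis.** The section on design, analysis and power states: "The primary analysis will be intent to treat, with data imputed one of two ways". In the first way, "all drop-outs will be assumed to not be performing SSE". The other is multiple imputation: "Second, we will create 5 imputed data sets for missing data based on all available data". The section does not say which result decides the trial or what happens if the two disagree. It expects retention of at least 60% at 4 months, gives no figure by arm, and plans no comparison of retention between arms.

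**The concern.** SSE is reported through the monthly surveys, so a woman who stops answering has no SSE data. If drop-outs are then scored as non-performers, the observed SSE rate in an arm is its retention multiplied by the SSE rate among those retained. A contact that keeps women answering surveys raises the observed rate even if it changes no one's skin checking.

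The plan calls this rule a worst case. Applied to both arms it is not conservative for the comparison: it favours whichever arm keeps more women. As written, one arm has an extra contact whose stated purposes include retention, and up to 40% loss is allowed for. If the drop-outs-as-zero analysis were taken as the result, an effect on survey completion could be reported as an effect on SSE.

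**Working it through.** **Inputs from the section on design, analysis and power.** About 500 women per arm; SSE 80% in control and 86.3% with intervention; autocorrelation 0.9; four monthly measures; retention at least 60%. Alpha is not stated for the primary test, so 0.05 two-sided is assumed. The 80% power given in the next sentence of the plan is taken to apply here too.

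**1. The plan's own figure.** Divide n per arm by the design effect for a mean of four measures.
- Compound symmetry: (1 + 3 × 0.9)/4 = 0.925. Effective n is 500/0.925 = 541, power for 80% vs 86.3% is 79.1%, and the detectable rate is 86.4%.
- AR(1): [4 + 2(3 × 0.9 + 2 × 0.81 + 0.729)]/16 = 0.881. Effective n is 567, power 81.0%, detectable rate 86.2%.

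The stated 86.3% reproduces, with all 1000 women and no allowance for drop-out.

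**2. Size of the transfer under drop-outs scored as no SSE.** Assume no true effect, with SSE 80% in both arms. At one time point:

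false difference = 0.8 × (intervention retention − control retention)

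A 5-point gap gives 0.8 × 5 = 4.0 points (48% vs 52%). A 10-point gap gives 8.0 points (48% vs 56%).

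If loss is spread evenly over months 1 to 4, the gap averaged over the four surveys is (1 + 2 + 3 + 4)/(4 × 4) = 0.625 of the month-4 gap. The transfer is then 0.8 × 0.625 = 0.5 points per point: about 2.5 points for a 5-point gap and 5.0 for a 10-point gap.

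**3. Chance of a significant result favouring the intervention, month-4 comparison, 500 per arm.**
- 5-point gap: standard error √(2 × 0.50 × 0.50/500) = 0.0316; 0.04/0.0316 = 1.26; Φ(1.26 − 1.96) ≈ 24%.
- 10-point gap: standard error √(2 × 0.52 × 0.48/500) = 0.0316; 0.08/0.0316 = 2.53; Φ(2.53 − 1.96) ≈ 72%.

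**4. Repeated-measures simulation.** 4000 trials per scenario, SSE 80% in both arms, correlation 0.9, drop-outs scored zero from the month of loss, cluster-robust test. The lower end of each range is steady loss; the upper end is all loss before month 1.

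| Retention, control / intervention | False difference (points) | Chance of false positive |
|---|---|---|
| 60% / 60% | 0 | 2.4–2.6% |
| 60% / 65% | 2.4–4.1 | 14–26% |
| 60% / 70% | 5.0–8.0 | 47–73% |

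**5. Gap needed to mimic the planned 6.3 points.** Single time point: 6.3/0.8 = 7.9 points. Steady loss: 6.3/0.5 = 12.6 points.

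**6. Sensitivity to the SSE rate.** If true SSE were 50%, a 10-point gap at month 4 gives 30% vs 35% and a 39% chance instead of 72%.

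**7. The second method.** Five-fold multiple imputation by arm, month-4 endpoint, drop-out unrelated to SSE within arm, 2000 simulated trials. For retention gaps of 0 to 15 points the bias was about zero and the one-sided error 2.3% to 2.8%.

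**The case against.** The strongest reply is that the same section lists multiple imputation, which does not carry a retention gap into the SSE contrast when drop-out is unrelated to SSE within arm. That stands. A reader might infer that the SSE effect cannot be separated from staying in the survey; the documents do not support so absolute a claim. What remains is that neither method is named as decisive.

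Nor do a few points of differential retention reproduce the 6.3-point target. That takes about 8 points at one time point and more than 10 under steady loss.

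The size and direction of any gap are also unknown. The arms share a survey email, texts, a brochure and postcard, follow-up of incomplete surveys, and survey payments that the plan does not split by arm. The written difference is one email. Intervention women also score moles and recruit a partner, and that burden could lower their retention, in which case the same rule would work against the intervention. A reader might infer that the plan favours the intervention; the documents do not establish that.

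Finally, the reminder's stated content is SSE, so it is partly the intervention itself, and the section on study interventions mentions only a text. Both points stand. The first is why the SSE prompts should stay; the second is a discrepancy to reconcile. Matching one email would not by itself equalise retention, so the missing-data rule needs attention as well.

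**Conclusion.** The concern holds in a limited form. Taking the section on procedures as written, only the intervention arm has an added reminder email, with retention among its stated purposes. In one of the two listed primary analyses, any retention difference between arms passes into the SSE contrast, at 0.8 points per point at a given month and about 0.5 when averaged over steady loss.

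With no true effect, 80% SSE, 500 per arm and 60% control retention, an assumed 5-point gain raises the chance of a false positive from 2.5% to between 14% and 26%, and an assumed 10-point gain to between 47% and 73%. A loss of retention in the intervention arm would bias the contrast the other way. The exposure reaches the trial's conclusion because the plan does not say which analysis governs. The control arm already has parallel materials (brochure, postcard, texts, mirrored survey), so the email is an avoidable gap in an otherwise matched design. It should be closed before enrolment, because contact cannot be matched afterwards.

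**What to change.** 1. Reconcile the study interventions and procedures sections on whether the intervention reminder is a text alone or an email and a text.
2. If the email stays, send controls a monthly healthy-lifestyle email matched in number and timing. Keep the SSE prompts as part of the intervention.
3. Send survey-completion reminders to both arms in identical wording and on the same schedule, separate from the SSE prompts.
4. Name multiple imputation by arm as the primary missing-data method. It rests on drop-out being explained by the data in the imputation model, so keep drop-outs-as-no-SSE as a sensitivity analysis and vary the SSE rate assumed for drop-outs separately in each arm.
5. Report survey completion by arm and month beside the primary result.

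The cost is one automated email template, an IRB wording change and a little more analysis.
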